#### 4.2.1.2 Other safety variables

The other safety variables are:

- Hematology, blood chemistry, endocrinology, and urinalysis parameters
- 12-lead electrocardiograms (ECGs)
- Vital sign measurements (blood pressure and pulse)
- Physical and neurological examination findings
- Body weight, height, and calculated body mass index (BMI)
- Tanner Stage (if applicable)
- Achenbach Child Behavior Checklist (CBCL) at Baseline for children 18 months and older (CBCL/1½-5 and CBCL/6-18) assessing behavior
- Bayley-III scales at Baseline for children <18 months of age at time of enrollment (applicable only to subjects enrolled in English-speaking countries)
- Cognitive function assessments (Behavior Rating Inventory of Executive Function® [BRIEF®]/BRIEF®-Preschool Version [BRIEF®-P]) (if applicable)
- LCM palatability and ease of use questionnaire

#### 4.2.2 PK variables

##### 4.2.2.1 Primary PK variables

No primary PK variables are defined for this study.

##### 4.2.2.2 Other PK variables

The other PK variables are:

- Plasma concentrations of LCM (for population PK analysis) and concomitant AEDs

#### 4.2.3 Efficacy variables

##### 4.2.3.1 Primary efficacy variables

No primary efficacy variables are defined for this study.

##### 4.2.3.2 Secondary efficacy variables

The secondary efficacy variables, based on daily seizure diaries, are:

- Percent change from Baseline in 28-day partial-onset seizure frequency
- $\geq 50\%$  reduction in 28-day partial-onset seizure frequency
- $\geq 75\%$  reduction in 28-day partial-onset seizure frequency
- Seizure days per 28 days (subjects with generalized seizures only)

- Seizure-free status

#### 4.2.3.3 Other efficacy variables

The other efficacy variables are:

- Clinical Global Impression of Change
- Caregiver Global Impression of Change
- Quality of life assessments (Pediatric Quality of Life Inventory [PedsQL™]) (if applicable)
- Health care resource use (concomitant AEDs, medical procedures, health care provider consultations not related to study, hospitalizations not related to study)
- All seizure frequency analyses as described in the secondary efficacy variables (presented for the overall Treatment Period only) may be additionally presented by modal daily dose group, by seizure type, by seizure classification subgroup, by time interval, by visit or time period, or by completer cohort

*Clinical Study Protocol, Section 4.3.3.1 (Potential drug-induced liver injury IMP discontinuation criteria). Original text, first, second, third, and fourth paragraphs:*

Subjects with potential drug-induced liver injury (PDILI) must be assessed to determine if IMP must be discontinued. In addition, all concomitant medications and herbal supplements that are not medically necessary should also be discontinued.

The PDILI criteria below require immediate and permanent discontinuation of IMP:

- Subjects with either of the following:
  - ALT or AST  $\geq 5$  xULN
  - ALT or AST  $\geq 3$  xULN and coexisting total bilirubin  $\geq 2$  xULN

The PDILI criterion below requires immediate discontinuation of IMP:

- Subjects with ALT or AST  $\geq 3$  xULN who exhibit temporally associated symptoms of hepatitis or hypersensitivity. Hepatitis symptoms include fatigue, nausea, vomiting, right upper quadrant pain or tenderness. Hypersensitivity symptoms include fever (without clear alternative cause), rash, or eosinophilia (ie,  $>5\%$ ).

The PDILI criterion below allows for subjects to continue on IMP at the discretion of the investigator.

- Subjects with ALT or AST  $\geq 3$  xULN (and  $\geq 2$  x Baseline) and  $<5$  xULN, total bilirubin  $<2$  xULN, and no eosinophilia (ie,  $\leq 5\%$ ), with no fever, rash, or symptoms of hepatitis (eg, fatigue, nausea, vomiting, right upper quadrant pain or tenderness).

*Was revised as follows:*

Subjects with potential drug-induced liver injury (PDILI) must be assessed to determine if IMP must be immediately and permanently discontinued. In addition, all concomitant medications and herbal supplements that are not medically necessary should also be discontinued.

The PDILI criteria below require immediate and permanent discontinuation of IMP:

- Subjects with either of the following:
  - ALT or AST  $\geq 5$ xULN
  - ALT or AST  $\geq 3$ xULN and coexisting total bilirubin  $\geq 2$ xULN
- Subjects with ALT or AST  $\geq 3$ xULN who exhibit temporally associated symptoms of hepatitis or hypersensitivity. Hepatitis symptoms include fatigue, nausea, vomiting, and right upper quadrant pain or tenderness. Hypersensitivity symptoms include fever (without clear alternative cause), rash, or eosinophilia (ie,  $>5\%$ ).

The PDILI criterion below requires discussion with the Medical Monitor to decide whether the subject is allowed to continue on IMP.

- Subjects with ALT or AST  $\geq 3$ xULN (and  $\geq 2$ x Baseline) and  $<5$ xULN, total bilirubin  $<2$ xULN, and no eosinophilia (ie,  $\leq 5\%$ ), with no fever, rash, or symptoms of hepatitis (eg, fatigue, nausea, vomiting, right upper quadrant pain or tenderness).

*Clinical Study Protocol, Section 4.4.1.2 (Subjects enrolling directly into SP848). Original text, first paragraph:*

Beginning with Protocol Amendment 4, at selected sites, up to approximately 100 eligible pediatric subjects  $\geq 4$  years to  $\leq 17$  years of age who have not previously participated in a LCM clinical study will be permitted to enroll directly into SP848. After Screening, eligible subjects will initiate treatment with LCM (oral solution or tablet, as chosen by the investigator and subject/caregiver), and the LCM dose will be titrated to a level to optimize tolerability and seizure control.

*Was revised as follows:*

Beginning with Protocol Amendment 4, at selected sites, up to approximately 100 eligible pediatric subjects  $\geq 4$  years to  $\leq 17$  years of age who have not previously participated in a LCM clinical study will be permitted to enroll directly into SP848. Beginning with local Protocol Amendment 5.2 for sites in Japan, approximately 46 eligible pediatric subjects  $\geq 4$  years to  $\leq 17$  years of age with partial-onset seizures who have not previously received LCM will directly enroll at approximately 9 sites in Japan. Beginning with local Protocol Amendment 5.4 for sites in China, approximately 60 additional eligible pediatric subjects with partial-onset seizures aged  $\geq 4$  years to  $\leq 17$  years, who have not previously participated in a LCM clinical study, will enroll directly into SP848. After Screening, eligible subjects will initiate treatment with LCM (oral solution or tablet, as chosen by the investigator and subject/caregiver), and the LCM dose will be titrated to a level to optimize tolerability and seizure control.

*Clinical Study Protocol, Section 4.4.1.4 (Study completion). Original text, first paragraph:*

At the completion of the study, investigators should discuss treatment options with the subject and/or their parent/legal guardian to best manage the subject's epilepsy. Taper of LCM may not be required for some subjects who complete the study depending on the treatment option selected by the investigator in consultation with the subject and/or parent/legal guardian. These subjects should complete Visit 13/Termination Visit and then complete the Safety Follow-Up telephone contact 28 to 35 days after Visit 13/Termination Visit. The Final Visit is not required for subjects who complete the study and who do not undergo taper of LCM.

*Was revised as follows:*

At the completion of the study, investigators should discuss treatment options with the subject and/or their parent/legal guardian to best manage the subject's epilepsy. Taper of LCM may not be required for some subjects who complete the study depending on the treatment option selected by the investigator in consultation with the subject and/or parent/legal guardian. These subjects should complete Visit 13/Termination Visit and then complete the Safety Follow-Up telephone contact 28 to 35 days after Visit 13/Termination Visit. The Final Visit is not required for subjects who complete the study and who do not undergo taper of LCM. The Safety Follow-Up Visit and the Safety Follow-Up telephone contact are not required for subjects who participate in EP0151 or EP0152.

*Clinical Study Protocol, Section 4.5 (Expected duration of the study). Original text, first paragraph:*

The maximum duration of LCM administration for an individual subject will be approximately 2 years.

*Was revised as follows:*

The maximum duration of LCM administration for an individual subject will be approximately 2 years or until approval of the marketing application (for Japan only), whichever comes first.

*Clinical Study Protocol, Section 5 (Treatment Procedures By Visit). Original text, first and second paragraphs:*

For all scheduled visits and telephone contacts (with the exception of the Safety Follow-Up telephone contact), a visit window of  $\pm 7$  days relative to Visit 1 is applicable. The Safety Follow-Up telephone contact will be performed 28-35 days after the last dose of LCM. A detailed tabular schedule of study procedures is provided in [Section 16.1](#). For further details of the assessments and the required procedures and methods, please refer to [Section 6](#), [Section 7](#), and [Section 8](#).

*Were revised as follows:*

For all scheduled visits and telephone contacts (with the exception of the Safety Follow-Up telephone contact), a visit window of  $\pm 7$  days relative to Visit 1 is applicable. The Safety

Follow-Up telephone contact will be performed 28-35 days after the last dose of LCM. The Safety Follow-Up Visit and the Safety Follow-Up telephone contact are not required for subjects who participate in EP0151 or EP0152.

Assessments will be done during monthly visits for the first 3 months, every 2 months for the remainder of Year 1, and every 3 months for Year 2. A detailed tabular schedule of study procedures is provided in [Section 16.1](#). For further details of the assessments and the required procedures and methods, please refer to [Section 6](#), [Section 7](#), and [Section 8](#).

*Clinical Study Protocol, Section 5.16 (Visit 13/Termination Visit [Week 96]). Original text, first paragraph:*

At the completion of the study, investigators should discuss treatment options with the subject and/or their parent/legal guardian to best manage the subject's epilepsy. Taper of LCM may not be required for some subjects who complete the study depending on the treatment option selected by the investigator in consultation with the subject and/or parent/legal guardian. These subjects should complete Visit 13/Termination Visit and then complete the Safety Follow-Up telephone contact 28 to 35 days after Visit 13/Termination Visit. The Final Visit is not required for subjects who complete the study and who do not undergo taper of LCM.

*Was revised as follows:*

At the completion of the study, investigators should discuss treatment options with the subject and/or their parent/legal guardian to best manage the subject's epilepsy. Taper of LCM may not be required for some subjects who complete the study depending on the treatment option selected by the investigator in consultation with the subject and/or parent/legal guardian. These subjects should complete Visit 13/Termination Visit and then complete the Safety Follow-Up telephone contact 28 to 35 days after Visit 13/Termination Visit. The Final Visit is not required for subjects who complete the study and who do not undergo taper of LCM. The Safety Follow-Up Visit and the Safety Follow-Up telephone contact are not required for subjects who participate in EP0151 or EP0152.

*Clinical Study Protocol, Section 5.19 (Final Visit). Original text, first paragraph:*

Subjects who complete the study or withdraw prematurely from the study, and who discontinue use of LCM (ie, taper), should complete the Final Visit 2 weeks after the final dose of study medication.

*Was revised as follows:*

Subjects who complete the study or withdraw prematurely from the study, and who discontinue use of LCM (ie, taper), should complete the Final Visit 2 weeks after the final dose of study medication. The Final Visit is not required for subjects who participate in EP0151 or EP0152.

*Clinical Study Protocol, Section 5.20 (Safety Follow-Up telephone contact). Original text, first paragraph:*

The Safety Follow-Up telephone contact is required for all subjects (those who complete the study as planned or have withdrawn prematurely from the study). For subjects who complete the study, this telephone contact will occur 28 to 35 days after Visit 13/Termination Visit (subjects who do not undergo taper of LCM) or 28 to 35 days after the last dose of LCM (subjects who discontinue use of LCM [ie, taper]). For subjects who withdraw prematurely from the study, this telephone contact will occur 28 to 35 days after the Early Termination Visit (subjects who do not undergo taper of LCM) or 28 to 35 days after the last dose of LCM (subjects who discontinue use of LCM [ie, taper]).

*Was revised as follows:*

The Safety Follow-Up telephone contact is required for all subjects (those who complete the study as planned or have withdrawn prematurely from the study) who do not participate in EP0151 or EP0152. For subjects who complete the study, this telephone contact will occur 28 to 35 days after Visit 13/Termination Visit (subjects who do not undergo taper of LCM) or 28 to 35 days after the last dose of LCM (subjects who discontinue use of LCM [ie, taper]). For subjects who withdraw prematurely from the study, this telephone contact will occur 28 to 35 days after the Early Termination Visit (subjects who do not undergo taper of LCM) or 28 to 35 days after the last dose of LCM (subjects who discontinue use of LCM [ie, taper]). The Safety Follow-Up telephone contact is not required for subjects who participate in EP0151 or EP0152.

*Clinical Study Protocol, Section 5.21(Study conduct due to coronavirus disease 2019 pandemic) was newly added as follows:*

The protocol-mandated visit schedule should be followed to the extent possible, considering the individual benefit-risk assessment by the investigator. If necessary, remote visits may be conducted and the subjects or caregivers will be contacted by telephone or videoconference. Remote follow-up, at minimum with a telephone call after 3 months, must be done (preferably more frequently and as needed to follow-up on participant safety assessments).

Ad hoc subject contact may be warranted to understand the current health status of the subjects, to follow up on AEs, and inform them of any protective measures taken by the clinical site as a result of the coronavirus disease 2019 (COVID-19) pandemic (eg, any measures that may limit access to the site or may require additional actions by the study participant prior to entry to the site).

If a subject needs to be discontinued and cannot come into the clinic, then appropriate tapering instructions will be provided, and a visit will be scheduled to perform safety assessments as soon as possible.

In situations where a subject is unable to return to the study site, investigators will assess and document the subject's safety via telephone contact. Based on information gathered from the telephone contact, investigators will confirm whether the subject could continue the current

study treatment based upon the outcome of the safety assessment. Subjects' agreement to implement this procedure should be obtained and documented prior to implementing any changes. Changes in the study treatment supply in this situation are described in Section 9.5.

If a subject visits another facility for a medical issue (or has to switch sites for a COVID-19-related reason), the investigator should request contact with the physician providing care to provide a detailed explanation of the subject's condition and his/her participation in the clinical study. Subjects or caregivers shall be reminded to completely collect and keep records of this visit.

Deviations to data collection including inability to perform some assessments, such as ECG, blood collection for safety laboratory assessments and PK, or alternative methods of assessment, such as phone calls, should be recorded in the source documentation and notated as "not done" in the eCRF.

In cases where subjects cannot return to the clinic, and it will not be possible to dispense a new seizure diary, subjects will be instructed to continue recording of seizures in a manner that is mutually agreed with the investigator (eg, hand-written notes, recording on a smart device). Any recording of seizures in a manner outside of the study seizure diary must be carefully documented in the source medical records (copies/print-screen printouts of these recordings will be brought to and retained at the site).

*Clinical Study Protocol, Section 6.2.1 (Clinical Global Impression of Change). Original text, first paragraph:*

The Clinical Global Impression of Change will be completed according to the tabular schedule of study procedures, [Section 16.1](#).

*Was revised as follows:*

The Clinical Global Impression of Change will be assessed at least once per year and be completed according to the tabular schedule of study procedures, [Section 16.1](#).

*Clinical Study Protocol, Section 6.2.2 (Caregiver Global Impression of Change). Original text, first paragraph:*

The Caregiver Global Impression of Change will be completed according to the tabular schedule of study procedures, [Section 16.1](#).

*Was revised as follows:*

The Caregiver Global Impression of Change will be assessed at least once per year and be completed according to the tabular schedule of study procedures, [Section 16.1](#).

*Clinical Study Protocol, Section 6.3 (Pediatric Quality of Life Inventory). Original text, first paragraph:*

The PedsQL is a validated instrument that consists of generic core scales suitable for use with pediatric populations, including those with acute or chronic health conditions (Varni et al, 2001; Varni et al, 2011). The PedsQL will be administered according to the tabular schedule of study procedures, [Section 16.1](#).

*Was revised as follows:*

The PedsQL is a validated instrument that consists of generic core scales suitable for use with pediatric populations, including those with acute or chronic health conditions (Varni et al, 2001; Varni et al, 2011). The PedsQL will be completed up to two times per year and will be administered according to the tabular schedule of study procedures, [Section 16.1](#).

*Clinical Study Protocol, Section 8.1.10 (Occurrence of COVID-19) was newly added as follows:*

Occurrence of COVID-19 in subjects should be reported as either “suspected COVID-19” or “confirmed COVID-19” along with all available relevant data including diagnostic and laboratory data. For subjects where COVID-19 is still suspected despite a negative viral test, please report as “suspected COVID-19” and provide relevant data to support the diagnosis as well as the test results.

*Clinical Study Protocol, Section 8.3 (Laboratory measurements). Original text, laboratory test table:*

Urinalysis	Hematology	Clinical chemistry		Endocrinology
Specific gravity	RBC	Total serum protein	Cholesterol	FSH
pH	WBC	Albumin	Triglycerides	LH
Albumin	Differential count	Calcium	Total bilirubin	Testosterone
Glucose	Platelet count	Phosphorus	Alkaline phosphatase	TSH
Ketone	Hemoglobin	Glucose	Creatinine	T3 (total and serum-free)
Microscopic exam for blood cells for casts/hpf	Hematocrit	Serum electrolytes (sodium, potassium, chloride, bicarbonate)	AST ALT GGT	T4 (total and serum-free)
		Uric acid	BUN	

*Was revised as follows:*

Urinalysis	Hematology	Clinical chemistry		Endocrinology
Specific gravity	RBC	Total serum protein	Cholesterol	FSH
pH	WBC	Albumin	Triglycerides	LH
Protein	Differential count	Calcium	Total bilirubin	Testosterone

Urinalysis	Hematology	Clinical chemistry			Endocrinology
Glucose	Platelet count	Phosphorus	Alkaline phosphatase		TSH
Ketone	Hemoglobin	Glucose	Creatinine		T3 (total and serum-free)
Microscopic exam for blood cells for casts/hpf	Hematocrit	Serum electrolytes (sodium, potassium, chloride, bicarbonate) Uric acid	AST ALT GGT BUN		T4 (total and serum-free)

*Clinical Study Protocol, Section 8.3.2 (Liver function tests and evaluation of PDILI). Original text, seventh paragraph:*

When IMP is stopped due to PDILI (as described in Section 4.3.3.1), IMP must be permanently discontinued unless a subsequent alternative diagnosis fully explains the hepatic findings.

*Was revised as follows:*

When IMP is stopped due to PDILI (as described in Section 4.3.3.1), IMP must be permanently discontinued.

*Clinical Study Protocol, Section 8.3.2.3 (Testing: identification/exclusion of alternative etiology). Original text, Table 8-2:*

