### **11.1 Case Report form completion**

This study is performed using remote data capture (RDC); the investigator is responsible for prompt reporting of accurate, complete, and legible data in the eCRFs and in all required reports. Any change or correction to the eCRF after saving must be accompanied by a reason for the change. Corrections made after the investigator's review and approval (by means of a password/electronic signature) will be reapproved by the investigator. The investigator should maintain a list of personnel authorized to enter data into the eCRF. Detailed instructions will be provided in the eCRF Completion Guidelines.

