The full-analysis set will be used for the analysis of seizure data and will consist of all subjects in the SS, who have at least 1 completed post-Baseline seizure diary.

*Clinical Study Protocol, Section 12.1.5 (Handling of protocol violators, drop-outs, and missing values). Original text, first paragraph:*

All data will be used to their maximum possible extent, but without any imputations for missing data for any parameter. Protocol deviations will be assessed during data review by a panel consisting of the study manager, the study biostatistician, a representative of the monitoring team, and other appropriate study team members.

*Was revised as follows:*

All data will be used to their maximum possible extent, but without any imputations for missing data for any parameter. Important protocol deviations will be reviewed as part of the ongoing data cleaning process and data evaluation. All important deviations will be identified and documented prior to database lock to confirm exclusion from analysis sets.

*Clinical Study Protocol, Section 12.2 (Determination of sample size). The following final paragraph was added:*

Beginning with Protocol Amendment 6, up to 75 eligible pediatric subjects  $\geq 4$  years to  $< 17$  years of age who have participated in EP0060 will be permitted to enroll into SP848.

*Clinical Study Protocol, Section 15 (References). The following references were added:*

Clinical Global Impression of Change, the Caregiver Global Impression of Change, quality of life assessments (Pediatric Quality of Life Inventory [PedsQL™]).  
<http://www.pedsql.org/PedsQL-CostStructure.pdf> and <http://plaza.umin.ac.jp/qol-research/>. Accessed on 10 July 2014.

Cognitive function assessments (Behavior Rating Inventory of Executive Function® [BRIEF®]/BRIEF® Preschool Version [BRIEF® P].  
<http://www4.parinc.com/Products/PermsLicensing.aspx?id=6> and  
<http://www4.parinc.com/products/PermsLicensing.aspx?id=8>. Accessed 10 July 2014.

Food and Drug Administration. Guidance for Industry. Drug-induced liver injury: premarketing clinical evaluation. US Dept of Health and Human Services, Center for Drug Evaluation and Research, Center for Biologics Evaluation and Research, 07/2009.

Kyoto International; Social Welfare Exchange Centre (KISWEC). Achenbach Child Behavior Checklist (CBCL) for children 18 months and older.  
<http://www.kiswec.com/aseba%20-%20order.html>. Accessed 10 July 2014.

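### Section 5.21, read literally, enters an assessment done by telephone in the eCRF as not done, the same entry as one that was missed

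*Protocol*

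**What the plan says.** Section 5.21 (Study conduct due to coronavirus disease 2019 pandemic) makes remote contact an intended mode: "If necessary, remote visits may be conducted and the subjects or caregivers will be contacted by telephone or videoconference". Where a subject cannot return to the site, "investigators will assess and document the subject's safety via telephone contact", and whether study treatment continues is confirmed on that basis.

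The data-entry instruction follows. Its subject is "Deviations to data collection including inability to perform some assessments, such as ECG, blood collection for safety laboratory assessments and PK", and the same sentence continues "or alternative methods of assessment, such as phone calls, should be recorded in the source documentation and notated as" *not done* in the eCRF.

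For families who cannot be given a new diary, the section asks them to go on recording seizures by another agreed means, such as written notes or a smart device. It adds: "Any recording of seizures in a manner outside of the study seizure diary must be carefully documented in the source medical records", with copies kept at the site. It says nothing about entering these counts in the eCRF.

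Three other places bear on this:

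- Section 11.1 (Case Report form completion): "the investigator is responsible for prompt reporting of accurate, complete, and legible data in the eCRFs and in all required reports".
- Section 12.1.5: all data are used as far as possible, with no imputation for any parameter.
- Section 12.1.1: the full-analysis set takes subjects from the Safety Set "who have at least 1 completed post-Baseline seizure diary".

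**The concern.** The sentence treats two different situations as one. An ECG or blood draw that could not happen is missing, and *not done* is the right entry. An assessment carried out by telephone is not missing; it has a date and a result. Giving it the same entry does two kinds of harm. The result is not in the database, and the record says that the assessment did not take place, so a count of missed assessments is also wrong.

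The statistical analysis plan cannot repair this. It works from what was entered, and two situations under one code cannot be separated afterwards without going back to source at each site.

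**Working it through.** The plan gives no figure here and none can be derived, so the check is a reading of the sections against one another.

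**1. What the sentence covers.** One subject (deviations to data collection) has two members: inability to perform an assessment, and alternative methods of assessment. One instruction applies to both: record in source, and mark *not done* in the eCRF.

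| Situation | Result exists? | eCRF entry under Section 5.21 | Correct description |
|---|---|---|---|
| Assessment not performed | No | *not done* | not done |
| Assessment performed by telephone | Yes, in source | *not done* | done, by telephone |

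The entry is right in the first row and wrong in the second.

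**2. Against Section 11.1.** The investigator owes accurate and complete eCRF data. In the second row the entry is neither. Section 11.1 makes no exception for the pandemic. It leaves detail to the eCRF Completion Guidelines, which are not part of the protocol.

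**3. Against Section 12.1.5.** Data are to be used as far as possible without imputation. A result held only in source cannot be used, and nothing stands in for it. The paragraph that Amendment 8 adds to Section 12.1.5 asks only that COVID-19 deviations be documented. It gives no rule for data obtained by another method.

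**4. What is exposed.** The telephone-contact columns of Tables 16-1 and 16-2 already schedule adverse event reporting, concomitant medications and concomitant AEDs. Telephone collection of these is planned, so it is not an alternative method. The exposed items are those scheduled for clinic visits only that could be obtained remotely, for example the C-SSRS, the global impressions, the questionnaires and health care resource use. Section 5.21 does not say which of these would be done by telephone, so the list is my assumption. The C-SSRS shows why the coding matters: under Section 4.3.3, certain answers on it require withdrawal. If it were given by telephone, such an answer would be in source while the eCRF said that the scale was not done.

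**5. Off-diary seizure records.** Section 5.21 requires documentation in source and copies at the site. That is ordinary source retention. It neither forbids nor requires eCRF entry, and Section 12.1.1 does not say whether such a record counts as a completed diary. This is silence on the point. The *not done* instruction is different, because it states a wrong entry.

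**The case against.** The best defence is a milder reading. Since the sentence is about deviations, what is marked *not done* may be only the in-clinic procedure, with the substitute described in source. That reading is possible, but the sentence does not say so, and sites that read it differently would code the same event differently.

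It is also fair to say that Section 5.21 presents remote contact mainly as safety follow-up, and that the study is open-label with descriptive summaries, so no hypothesis test is affected. Both points limit the consequence; neither makes the entry correct.

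A reader might go further and infer any of the following. The documents do not support them.

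- *That valid data never reach the database.* This is too absolute. Adverse events and medications have a scheduled telephone route, Section 8.1.10 requires COVID-19 cases to be reported, and keeping copies of seizure notes at the site does not stop anyone from transcribing them.
- *That off-diary periods count as zero seizures.* Section 12.1.4.1.1 divides seizures by the days in the interval. It does not say that days without diary data stay in the denominator with no seizures, and Section 12.1.5 rules out imputation. The counting of evaluable days can be left to the statistical analysis plan.
- *That subjects drop out of the full-analysis set.* One completed post-Baseline diary is enough, so anyone who completed a study diary before losing access already qualifies.

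**Conclusion.** The point holds for the data-entry sentence. Section 5.21 as written gives a completed remote assessment the entry of a missed one, contrary to Sections 11.1 and 12.1.5. For off-diary seizure counts there is only an omission, which is worth closing in the same edit.

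The size is unknown. The protocol does not state how many visits were or would be remote, or which assessments would be done remotely, so any share of follow-up lost would rest on invented inputs. The primary variables (TEAEs, SAEs and withdrawals due to TEAEs) are largely protected by the scheduled telephone route. The exposure lies in the other safety and efficacy variables collected at clinic visits.

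The conclusion assumes that sites follow the sentence literally and that the eCRF Completion Guidelines do not override it. It rests on Section 5.21 as set out in Amendment 8, the last amendment listed.

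**What to change.** Rewrite the sentence so that *not done* is used only for an assessment not performed by any mode. Any assessment performed remotely is entered in the eCRF with its date, result and mode of collection (clinic, telephone or video). In the same paragraph, state that seizure counts recorded outside the study diary, and the days they cover, are transcribed to the eCRF with a flag for their source.

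The cost is one revised paragraph, a mode and source flag in the eCRF, matching text in the completion guidelines, and some data entry at sites. Because the source records are kept, assessments already coded *not done* can be corrected from them. The downside is mixed-mode data, which the flag identifies. Whether to repeat any summary without remote data can be left to the statistical analysis plan.
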